## **OBJECTIVES:**

The specific aims of this proposal are:

**Aim 1:** To determine whether targeting blood pressure to a level above an individual's lower CBF autoregulatory threshold during CPB (cardiopulmonary bypass) reduces the frequency of the composite end-point of clinical stroke, or a diffusion-weighted MRI brain lesion, or postoperative cognitive decline 4 to 6 weeks after surgery, compared with patients who receive standard empiric blood pressure management. **Hypothesis:** Targeting mean arterial pressure during CPB to a level above an individual's lower autoregulatory threshold reduces the risk for brain injury in patients undergoing cardiac surgery.

**Aim 1a:** To assess whether extracranial and/or intracranial arterial stenosis (detected by MR angiography), or other patient characteristics such as age, gender, hypertension, diabetes, or prior stroke, modify the effect of maintaining blood pressure above an individual's lower CBF autoregulatory threshold on the risk for the above composite neurological outcome. **Hypothesis:** Targeting blood pressure during CPB to a level above an individual's lower autoregulatory threshold reduces the risk for brain injury in patients undergoing cardiac surgery who have extra- and/or intra-cranial arterial stenosis.

**Aim 1b:** To assess whether targeting MAP to a level above an individual's lower CBF autoregulatory threshold during CPB reduces the frequency of cognitive decline 1 year after surgery compared with the use of standard blood pressure management.

**Aim 2:** To compare three methods of continuous monitoring of CBF autoregulation derived from the linear regression correlation between cerebral oximetry O2 saturation and blood pressure (oximetry index), near infrared-derived relative total hemoglobin and blood pressure (hemoglobin volume index), and transcranial Doppler measured CBF velocity and blood pressure (mean velocity index). **Hypothesis:** Mean velocity index, cerebral oximetry index, and hemoglobin volume index provide complimentary data on detecting the lower limit of CBF autoregulation.

Aim 2 has been satisfactorily addressed and will no longer be an aim of this project.

**Aim 3:** To evaluate whether perioperative transcranial Doppler measurements of major cerebral artery blood flow velocity can identify patients prone to the composite neurological end-point. **Hypothesis:** Perioperative transcranial Doppler examination can

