**Aim 1b: To assess whether targeting MAP to a level above an individual's lower CBF autoregulatory threshold during CPB reduces the frequency of cognitive decline 1 year after surgery compared with the use of standard blood pressure management.** In Aim 1, we will test whether the Intervention and Control groups have the same risk of the primary composite neurologic endpoint of stroke, DWI lesion, or cognitive decline 4 to 6 weeks after surgery (i.e., null hypothesis). This will be done using a two-sided test of proportions at 5% significance level. We will first calculate and report the relative risk (RR) of composite neurologic outcome by comparing the Intervention and Control groups without adjusting for any potential confounders (i.e., the unadjusted RR). In addition, we will construct an adjusted estimate of RR using a generalized linear model (GLM) with Poisson distribution and robust standard errors. The candidate models will include study group as the primary independent variable as well as extra- or intracranial arterial stenosis determined by MRA, patient age, gender, and baseline risk factors that are assumed to be highly predictive of the outcome, such as history of hypertension, diabetes, or prior stroke. To assess potential effect modification by cerebral arterial stenosis, age, gender, hypertension, diabetes, or prior stroke (Aim 1a), we will calculate the unadjusted RR stratified by these variables. We will use a test of homogeneity to compare stratum-specific estimates of RR. Finally, we will use the model developed in Aim 1 to report stratum-specific adjusted estimates of RR by introducing appropriate interaction terms of these variables and study group in the GLM model. We will compute the Z-score for the cognitive tests to normalize the distribution to the control data. The individual Z-scores will be combined into an average score and re-normalized. To assess postoperative change in cognitive function for up to 1 year (Aim 1b), we will use population-average marginal models estimated using generalized estimating equations (GEE) with exchangeable working correlation structure. The model will include assessment time with 2 indicator variables for 1 year and 4 to 6 weeks postoperation and baseline as the reference group as well as Intervention Group, and their interaction to test whether postoperative trajectory of cognitive function differs by group.

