Our current enrollment trajectory suggests that at least 277 patients will have undergone the protocol of our study before the end of the funding period for the initial grant. At that point we would expect to have 101 patients who have undergone MRI for evaluation of DWI lesions. An additional 143 patients with complete MRI, stroke, and cognitive endpoint data are needed to reach the target of 244 patients with the primary, complete endpoint data. To reach this target, we will need to enroll an additional 350 patients in this renewal. Our recruitment projections for our initial funded study are a conservative estimate, as we have enrolled 277 patients to our study (101 have MRI data). On average, 5 to 8 patients are enrolled per month. These projections confirm that the plan for this submission of studying 350 additional patients (a total of 630 patients) will ensure completion of the study with 244 patients having all study assessments, including MRI, at the completion of the proposed study funding period.

In addition, we calculated the minimal sample size required to detect 0.2 SD difference in combined Z-score for cognitive tests normalized to the control group's data between the Intervention and Control groups with 80% power . We assume 2 follow-up points (4 to 6 weeks and 1 year after surgery) and an average within-patient correlation of 0.7 (observed in our preliminary data). The calculations indicate that we will need 177 observations per group, or 354 patients in total, to detect 0.2 SD difference with 80% power (assuming 5% Type I error). The study (first and second funding periods) will recruit a total of 489 patients to meet the MRI endpoint. Therefore, we will meet our goal of having 354 patients to detect the expected 0.2 SD difference in combined cognitive score seven with a 1-year drop-out rates high as 27%. Historically, the drop-out rate for cognitive testing at 1 year in similar populations has been between 3% and 24% .

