As of June 2016, we have enrolled 280 patients in the first five years and 244 patients in the second five year study. We need approximately 150 patients to complete enrollment.

In addition, we calculated the minimal sample size required to detect 0.2 SD difference in combined Z-score for cognitive tests normalized to the control group's data between the Intervention and Control groups with 80% power. We assume 2 follow-up points (4 to 6 weeks and 1 year after surgery) and an average within-patient correlation of 0.7 (observed in our preliminary data). The calculations indicate that we will need 177 observations per group, or 354 patients in total, to detect 0.2 SD difference with 80% power (assuming 5% Type I error). The study (first and second funding periods) will recruit a total of 489 patients to meet the MRI endpoint. Therefore, we will meet our goal of having 354 patients to detect the expected 0.2 SD difference in combined cognitive scores even with a 1-year drop-out rate as high as 27%. Historically, the drop-out rate for cognitive testing at 1 year in similar populations has been between 3% and 24%.

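### The 177 per group (354) for the cognitive Z-score is right only for change averaged over both follow-ups, which the plan does not specify, and the 27% drop-out margin rests on an enrolment total (489) that the plan contradicts

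*Combined protocol and SAP*

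**What the plan says.** The sample-size justification (printed after Rapid Dissemination of Clinical Research, with the cognitive paragraph given twice) says that "we will need 177 observations per group, or 354 patients in total, to detect 0.2 SD difference with 80% power". Its inputs are a 5% Type I error, an average within-patient correlation of 0.7, and two visits: "We assume 2 follow-up points (4 to 6 weeks and 1 year after surgery". It names neither the contrast nor the formula. It adds that the study "will recruit a total of 489 patients to meet the MRI endpoint", so the 354 would be reached "even with a 1-year drop-out rate as high as 27"%. Historical 1-year loss is given as 3% to 24%.

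The analysis is described elsewhere:

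- Objectives, Aim 1b: whether the intervention "reduces the frequency of cognitive decline 1 year after surgery compared with the use of standard blood pressure management".
- Study Statistics: "To assess postoperative change in cognitive function for up to 1 year (Aim 1b"), a GEE model with an exchangeable working correlation, two visit indicators (baseline as reference), group, "and their interaction to test whether postoperative trajectory of cognitive function differs by group".
- Statistical Analysis Plan: the cognitive outcome is change from baseline at 4 to 6 weeks.

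On enrolment, the same sample-size text plans on "studying 350 additional patients (a total of 630 patients"). It also reports, as does Study Timelines, 280 + 244 patients enrolled by June 2016 and about 150 still needed.

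**The concern.** A power statement has meaning only for a named comparison. Here the inputs mention two follow-ups, the aim mentions one, and the model tests two interaction terms jointly. These comparisons have different variances, so one sample size cannot give 80% power for all of them. The 27% margin is simply the loss that takes 489 down to 354, so it inherits whatever contrast lies behind 354. Its base, 489, had already been passed by June 2016.

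At stake is how a null 1-year cognitive result is read. A reader who takes the paragraph at face value would credit the 1-year comparison with 80% power at 354 patients and with tolerance of 27% loss.

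**Working it through.** **Inputs.** From the sample-size text: difference 0.2 SD, 80% power, 5% Type I error, two follow-ups, correlation ρ = 0.7, equal arms. Assumed: a two-sided test (stated for Aim 1) and the same ρ for every pair of visits (matching the exchangeable working structure). A one-sided averaged-change test gives 140 per group and does not match.

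**Reproducing 177.** n per group = 2(1.96 + 0.8416)²·v / 0.2² = 392.4·v, where v is the variance of the outcome relative to one score.

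| Outcome | v | n per group |
|---|---|---|
| Change, averaged over both follow-ups | (1+ρ)/2 + 1 − 2ρ = 0.45 | 176.6 → **177** |
| Change at 1 year | 2(1−ρ) = 0.60 | 235.5 → 236 |
| Baseline-adjusted 1-year score | 1 − ρ² = 0.51 | 201 |
| Baseline-adjusted average | (1+ρ)/2 − ρ² = 0.36 | 142 |
| Raw follow-up average | (1+ρ)/2 = 0.85 | 334 |
| Raw single visit | 1 | 393 |

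Only averaged change gives 177.

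**1-year change at 177 complete cases per group.** 0.2/√(2 × 0.60/177) = 2.429; Φ(2.429 − 1.96) = 68%. The plan gives only an average correlation. Suppose the baseline to 1-year value is 0.65 or 0.75, the baseline to 4–6-week value is 0.75 or 0.65 correspondingly, and the follow-ups correlate 0.7. The average is still 0.7 and averaged change still needs 177. Then v = 0.70 or 0.50, power is 61% or 76%, and 80% needs 275 or 197 per group.

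**Joint interaction (2 df) at 177 per group.** The two change scores have covariance S = [[0.6, 0.3], [0.3, 0.6]]. Noncentrality is (177/2)·δ′S⁻¹δ.

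- δ = (0.2, 0.2), or 0.2 at one visit and 0 at the other: δ′S⁻¹δ = 0.0889, noncentrality 7.87, power 71%; 217 per group for 80%.
- δ = (0.1, 0.2): 0.018/0.27 = 0.0667, noncentrality 5.90, power 58%; 290 per group for 80%.

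**The drop-out margin.** 1 − 354/489 = 27.6%, and 489 × 0.73 = 357, so the 27% is the loss that leaves 354. Assume ignorable loss at 1 year only, with drop-outs keeping their baseline and 4–6-week scores. At 489 recruits and 27% loss, power is then:

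| Contrast | Power |
|---|---|
| Averaged change, longitudinal model | about 88% |
| Interaction, 0.2 at both visits, longitudinal | 82% |
| Interaction, 0.2 at 1 year only, longitudinal | 72% |
| Interaction, 0.1 then 0.2, longitudinal | 63% |
| 1-year change, longitudinal | 72% |
| 1-year change, complete cases | 68% |

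For 80% power on the 1-year change from 489, complete cases tolerate 1 − (2 × 235.5)/489 = 3.7% loss; the longitudinal model tolerates about 5%.

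**Enrolment totals.** 280 + 350 = 630. 280 + 244 = 524, and 524 + 150 = 674; that last sum is not a total printed in the plan. Both exceed 489.

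| Recruits | 1-year power at 24% loss (complete cases / longitudinal) | At 27% loss | Loss tolerated for 80% |
|---|---|---|---|
| 630 | 81% / 83% | 79% / 82% | 25% / 32% |
| 674 | 83% / 86% | 82% / 85% | 30% / 38% |

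Over the same totals and losses, the interaction has about 82 to 93% if the effect is at both visits or at 1 year only, and about 70 to 79% if it is 0.1 then 0.2.

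**The case against.** The strongest defence is that 177 is correct. Two follow-ups are listed beside a single 0.2 SD difference, which points to a calculation using both visits; the Aim 1b analysis covers change up to 1 year; and the planned GEE can yield the averaged contrast without refitting. All of that stands, so a reader who infers an arithmetic error goes too far. But the contrast has to be recovered by trial, since the text never names it. Nor can it be looked up: the reference number attached to the calculation leads, in the list, to a rat imaging paper.

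A second defence is that 177 complete cases is not the plan's scenario. GEE and random-effects models (Missing data section) keep earlier scores from drop-outs, and with 489 recruits and 27% loss the interaction reaches 82% if the effect is present at both visits. That also stands, but only for that effect pattern; it does not rescue the 1-year contrast (72%).

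Third, the replacement figures are conditional too. The 68% and 236 need equal correlations, and the 71% and 217 need particular effect patterns. This is fair, so the ranges belong with them.

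Finally, a reader might infer that the trial is underpowered for Aim 1b. The documents do not support that. The outdated 489 understates recruitment, and at 630 to 674 the 1-year contrast has about 79 to 86% power at 24 to 27% loss.

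**Conclusion.** The concern holds as a mismatch between a stated figure and the planned analysis, for a secondary aim. The 177 per group gives 80% power for mean Z-score change averaged over both follow-ups and does not carry over to the 1-year question (about 68%; 61 to 76% over the correlation range shown) or to the interaction (71% or 58% by effect pattern). The 27% margin likewise does not hold for the 1-year contrast at 489. These figures rest on a 0.2 SD effect, a two-sided 5% test, correlations averaging 0.7, and, for the longitudinal results, ignorable loss at 1 year only.

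The conflict over 489 needs no such assumptions; it is plain from the text. Correcting it helps the trial, because the larger totals support the 1-year comparison better than the paragraph's own base does. All these calculations concern a mean, whereas Aim 1b is worded as a frequency of decline, so none of them gives the power of a binary 1-year test.

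**What to change.** In both copies of the cognitive sample-size paragraph:

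1. Name the Aim 1b contrast being powered and give its power or size with the assumed effect pattern and correlations. With all correlations 0.7, that is 236 per group for the 1-year change. For the joint interaction it is 217 per group (0.2 SD at both visits or one only) or 290 (0.1 and 0.2). Alternatively, keep 177 and add the averaged contrast to the Aim 1b analysis in Study Statistics.
2. Say that the figure is for mean Z-score change and not for the frequency of decline; a binary 1-year test would need its own figure.
3. Replace 489 with one reconciled enrolment total, used throughout, and recompute the drop-out tolerance for the named contrast.

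This is a change of wording, with no new patients or data. The only downside is a less favourable stated power at 354 if the 1-year contrast or the interaction is chosen.

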## Missing data

Two sources of missing data are anticipated: missing data on predictors and missing data on the primary outcome. The strategy of dealing with missing data on predictors will depend on the amount of missing data. If the overall number of observations with missing predictors is under 5%, a complete-case analysis will be performed by dropping observations with missing data. The pattern of missingness will be examined. If the amount of missing data is between 5% and 20%, we will calculate the main results based on the complete-case analysis, but we will perform a sensitivity analysis using multiple imputation strategy. No attempt will be made to impute variables that have more than 20% data missing. Missing data on outcomes and the drop-out pattern will be assessed. No imputation of the outcome variables will be attempted. In addition to the primary analysis with the GEE approach, random-effects models have been shown to be a useful strategy in cases of non-equal number of measurements across individuals if missing data mechanism can be assumed to be ignorable. Therefore, the primary analysis will be supplemented by the random-effects approach. In addition, we will explore random-effects pattern mixture models to assess the influence of missing data in these analyses.

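### The primary composite is sized on complete data from 38.7% of enrolled patients, a subset formed after randomisation, with no planned sensitivity analysis for the rest; the stated enrolment also does not deliver that number

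*Combined protocol and SAP*

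**What the plan says.** The sample-size justification (Study Statistics, after Rapid Dissemination of Clinical Research) asks for 122 patients per arm with MRI, for 80% power to detect 45% versus 27%. It describes these patients as having every endpoint component: "An additional 143 patients with complete MRI, stroke, and cognitive endpoint data are needed to reach the target of 244 patients". On yield it reports "as we have enrolled 277 patients to our study (101 have MRI data". On enrolment it states that "studying 350 additional patients (a total of 630 patients) will ensure completion of the study with 244 patients having all study assessments". The Aim 1b calculation that follows gives a different total: "The study (first and second funding periods) will recruit a total of 489 patients to meet the MRI endpoint". A later update reads "As of June 2016, we have enrolled 280 patients in the first five years and 244 patients in the second five year study", with about 150 more still needed.

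The Missing data section expects missing primary-outcome data. It says "Missing data on outcomes and the drop-out pattern will be assessed", and then "No imputation of the outcome variables will be attempted". Its multiple-imputation sensitivity analysis covers predictors only, with a limit: "No attempt will be made to impute variables that have more than 20% data missing". The random-effects and pattern-mixture models are offered as supplements to the GEE analysis. Under Aims 1 to 1b, GEE is used for the repeated cognitive score. The composite gets a test of proportions and a Poisson model with robust errors.

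**The concern.** Patients are randomised before bypass (Patient Randomization). The section COx and Clinical Outcomes says the obstacles to MRI become known only after surgery. They include retained pacing wires and scanner availability, but also level of illness and death. Experimental Problems lists death and severe stroke among reasons for missed 4–6 week testing. The evaluable subset is therefore formed after randomisation, and partly by matters related to the outcome. The neurologic evaluation text adds a pull the other way, because MRI is ordered when stroke is likely.

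Critical care doctors are told the pressure threshold for Intervention patients (Autoregulation Monitoring), and no section says who judges fitness for MRI. Scanning that differs by arm cannot be ruled out.

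The plan never names the analysis set for the composite. Sizing on complete cases and barring outcome imputation together imply a complete-case analysis. That would drop patients with a known component event, such as a stroke shown on CT, who had no research MRI. Deaths are not classified. At stake is whether the primary result can be read as a comparison of the randomised groups.

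**Working it through.** **1. The plan's own figure.** Inputs: p1 = 0.45, p2 = 0.27, mean 0.36, two-sided 5%, 80% power.
- Uncorrected: n = [1.96·√(2×0.36×0.64) + 0.842·√(0.45×0.55 + 0.27×0.73)]² / 0.18² = 110.4 per arm.
- With continuity correction: (110.4/4)·[1 + √(1 + 4/(110.4×0.18))]² = 121.3, so 122 per arm. This reproduces the stated figure. Aim 1 names no correction, so power is given both ways below.

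**2. Size of the gap.** 244/630 = 38.7%, so 386 (61.3%) lack the complete endpoint. The documents give no separate count of randomised patients, so enrolled is taken as randomised.

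**3. Outcome-related scanning (illustration; no scan rates by arm are given).** Assume no true effect, 45% events in both arms and 39% scanned. One arm scans its event patients at a rate s instead of 39%. Its observed event rate is 0.45s / (0.45s + 0.55×0.39).

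| s | observed rate | apparent RR | overall scan rate, that arm |
|---|---|---|---|
| 0.34 | 41.6% | 0.93 | 36.75% |
| 0.29 | 37.8% | 0.84 | 34.5% |
| 0.44 | 48.0% | 1.07 | 41.25% |
| 0.49 | 50.7% | 1.13 | 43.5% |

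With 122 per arm, the uncorrected 5% test rejects about 8% of the time in the first row and 21% in the second. Overall scan rates then differ by only 2.2 and 4.5 points.

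**4. Tipping point (illustration).** Take 315 per arm, 122 observed at 45% versus 27%, and 193 missing. If missing patients have 45% risk in both arms, the all-randomised rates are 45% and (122×0.27 + 193×0.45)/315 = 38.0%: RR 0.85, z = 1.78, no longer significant. The effect vanishes if missing Intervention patients carry 122×0.18/193 = 11.4 points more risk than missing controls.

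**5. The counting rule alone.** Assume random scanning at 38.7%, independent components, and each component reduced by 40%. Component rates come from Detection of Brain Injury.
- Low ends (stroke 2%, decline 18%, DWI 26%): complete-case control rate is 1 − 0.98×0.82×0.74 = 40.5%, Intervention 1 − 0.988×0.892×0.844 = 25.6%, RR 0.63. Counting unscanned patients as lesion-free gives 0.62. Keeping recorded events and leaving out other unscanned patients gives 0.68.
- High ends (5%, 40%, 56%): 0.68, 0.65 and 0.77.

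The main risk is therefore outcome-related scanning more than the rule.

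**6. Yield.** 101/277 = 36.5%. Needed: 244 − 101 = 143 of 350 = 40.9%. Expected with MRI: 101 + 350×0.3646 = 228.6, or 630×0.3646 = 229.7. The chance of reaching 244 is 5.0% (binomial, 143 of 350), 12.7% (binomial, 244 of 630), or 13.9–15.9% when uncertainty in the yield is included (beta-binomial, 143 of 350 to 353).

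The update implies 280 + 244 + 150 = 674, and 674×0.3646 = 245.8 with MRI. The chance of at least 244 is then 56–59%. No 4–6 week cognitive loss is stated. At an assumed 3–10%, 674 gives 238–221 complete, and 244 complete needs 244/(0.3646×0.97) = 690 to 244/(0.3646×0.90) = 744 enrolled. At 36.5%, 489 gives 178.

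| complete patients | power, corrected | power, uncorrected |
|---|---|---|
| 244 | 80.3% | 83.8% |
| 229 | 77.4% | 81.4% |
| 246 | 80.6% | 84.1% |
| 238 | 79.2% | 82.9% |
| 221 | 75.8% | 80.0% |

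**The case against.** The complete-case analysis is an inference. Aim 4 restricts its analysis set explicitly and Aim 1 does not. The composite is joined by or, so a CT-proven stroke already meets it. This narrows the defect to an unstated analysis set, but it does not say what happens to an unscanned patient with no recorded event, or to a death.

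The selection illustration may be too strong. Most DWI lesions are clinically silent, and cognitive decline is measured after the scan, so stroke (about 2–5%) is the component visible at scanning. If one arm scanned no stroke patient at all, scanning of event patients would fall by 0.39×2/45 = 1.7 or 0.39×5/45 = 4.3 points, giving RR 0.975 or 0.94 and rejection of 5.4% or 7.4%. This stands as a limit on the stroke route alone, and a 10-point gap is not small. General illness that goes with silent lesions could add to it, and the documents give no figures to bound that.

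There are safeguards: blinded assessors, analysts and image readers, escorted transport of ICU patients to the scanner, scanning with pacing wires when necessary, and an MRI payment. They help, but none tests the result against missing data.

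On yield, 40.9% lies within the exact 95% interval for 101/277 (30.8% to 42.4%). The older count of 82 MRIs among 176 patients (46.6%) would give 101 + 163 = 264. Table 1 totals 196, and 41.8% would still give 101 + 146 = 247. So 630 is optimistic, not impossible. But 101/277 is the larger count, stands beside the assurance, and counts MRI only.

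**Conclusion.** The concern holds. The plan expects about 61% of enrolled patients to lack the complete primary endpoint, partly for outcome-related reasons arising after randomisation. It bars outcome imputation and plans no sensitivity analysis for the composite. The size and direction of any bias are unknown: the RR figures above rest on assumed scan rates and show what could happen, not what has happened. This must be settled before the data are unblinded.

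The yield is a smaller point. The assurance of 244 from 630 does not follow from the 36.5% reported beside it. The shortfall is about 15 patients, with power of 77% corrected or 81% uncorrected. The update to about 674 roughly restores 244 with MRI but leaves almost no margin for missed cognitive tests, and 489 is out of date because 524 were already enrolled by June 2016.

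A minor related item is that MRA stenosis, a candidate covariate for the adjusted RR, is collected at the MRI visit. It costs a complete-case analysis nothing, but under the 20% limit it rules out an adjusted RR in all randomised patients.

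**What to change.** 1. State the primary analysis set in advance. Complete-case may stay primary. Add a prespecified analysis of all randomised patients in which any recorded stroke, DWI lesion or cognitive decline counts as an event whether or not MRI was done, and state how deaths are classified. Unscanned patients with no recorded event have unknown status and go to item 2.
2. Amend the bar on outcome imputation to allow a sensitivity analysis of the composite: multiple imputation within arm of missing DWI and cognitive status from variables actually collected, plus a tipping-point analysis, shown beside the complete-case result. Report MRI and cognitive-test completion by arm, with reasons where known.
3. Base the main adjusted RR on baseline covariates available for everyone, and move MRA stenosis to a secondary model in scanned patients.
4. Replace 489 and 630 with one current total. Restate expected completers and power at the observed MRI yield, with an allowance for missed 4–6 week tests.

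The cost is SAP wording and analysis time, with no new patient assessments. With about 60% of DWI status missing, the imputed result depends on the model and should remain a sensitivity analysis. The documents do not say that the reason for a missing MRI is recorded per patient, so chart abstraction may be needed. The stated power becomes less favourable, or enrolment must rise.
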